Aim 1. Measure impact of apps on access to dermatology care. *San Francisco VA Health Care System's involvement is limited in Aim 1. All data related to this aim is collected by the VA's Center for Access Policy, Evaluation Research (CAPER) located at the Boston VA Health Care System. All data collected from the Corporate Data Warehouse, or any other databases as approved by the Boston VA Health Care System IRB will be anonymously recorded, aggregated, and shared with investigators and study staff at the San Francisco VA Health Care System and other sites. No analysis of the primary data will occur at San Francisco VA.*

Both apps will be made available over a 2 year period in a randomized, stepped-wedge design to Veterans Health Administration (VHA) facilities, after each app becomes available. The *VA Telederm* app will be distributed to 36 eligible VHA facilities that currently have low teledermatology activity and thus have had relatively poor adoption of basic consultative teledermatology. The *My Telederm* app will be distributed to 24 facilities with dermatology clinics that currently have relatively high teledermatology activity and thus already have relatively mature teledermatology programs ready for advanced operations.

By using health factors and stop codes unique to each app, we will use the VA Corporate Data Warehouse (CDW) to measure the impact of both apps on the following outcomes reflecting dermatology access: 1) Consult and appointment completion times for both teledermatology and in-person consults, stratified by new and established patients (primary outcome); 2) Instances of

dermatologic care (associated with either teledermatology or in-person dermatology encounters); and 3) Travel costs for VA, as well as non-VA care consult rates and associated costs. In addition, the following outcomes will be measured specifically for the *My Telederm* app: 1) Proportions of new patient encounters in-person dermatology clinics; and 2) “No-show” rates and timeliness of follow-up. Results of each of these access measures will be stratified to examine the effect on rural/highly rural Veterans, as well as to determine whether a differential effect occurs for facilities with some pre-existing teledermatology relative to those that had none.

Aim 2. Determine the factors that affect personal and organizational adoption of mobile apps.

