Using the Replicating Effective Programs framework, we will work with OCC to implement and measure the deployment, adoption and utilization of both teledermatology apps throughout all eligible VA sites. In one sub-aim, which is the principal focus of the current IRB application, we will conduct a formative evaluation of the implementation process at 3 early adopter sites to develop implementation strategies to guide subsequent nationwide deployment and research. Surveys and semi-structured interviews will assess Organizational Readiness for Change (ORC) at these sites regarding the apps, and link ORC to stages of implementation, barriers and facilitators to implementation, and implementation effectiveness as measured by uptake of the apps and actual use of teledermatology.

In the second sub-aim, we will also monitor deployment, adoption and utilization of both teledermatology apps nationally by analyzing remotely accessible data from the CDW and OCC. The primary data will be collected by CAPER under its own IRB approval, and aggregate data will be shared with the PIs and co-investigators. We will then correlate the degree of adoption with reach of the program (i.e., number of Veterans served) and stratify analyses of primary outcomes from Aim 1 based on degree of adoption.

At the conclusion of the project, we expect to document important indicators of mobile teledermatology’s effects on patient access in the nation’s largest healthcare system and to comprehensively understand the implementation of mobile teledermatology. These novel achievements will guide future mobile telemedicine endeavors in VA, and will inform other large healthcare organizations interested in telehealth.

8.3 DESIGN: Briefly describe the study design (e.g., observational, interventional, randomized, placebo-controlled, blinded, cross-over, cross-sectional, longitudinal, pharmacokinetic, etc.):

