Validate a new model for enhancing access to patients. Historically, teledermatology has been principally practiced as a consultative tool where a PCP requests guidance from a dermatologist. The preponderance of published research has similarly focused on consultative teledermatology. However, with the widespread availability of digital cameras and internet access, the ability to accept teledermatology consultations directly from patients has increasingly emerged in commercial ventures but with little scientific validation of their actual impact on healthcare. Within VA, there has also recently been an evolution toward delivering healthcare centered in patients' homes, and OCC has begun live-interactive telehealth encounters with patients in their homes. The effect of this type of telehealth is unknown. The *My Telederm* app will be VA's first attempt to bring store-and-forward telehealth into patients homes and may have significant impacts on not only the patients that it directly serves, but also indirect effects on new patients who need to be seen in person in clinics and who may benefit from the additional capacity created by allowing established patients to follow-up remotely. The proposed research seeks to measure the magnitude of this effect.

Understand factors affecting successful implementation of mobile apps. Implementation and adoption of telehealth, including teledermatology, in the VHA has proven to be a slow and heterogeneous effort, having taken over 8 years since the program was nationally disseminated by VA, with no systematic effort to collect data that would inform VA as to the reasons why teledermatology has been actively adopted and thriving at some sites, while being neglected or failing at others. It is thus significant that the proposed research will be the first large-scale attempt to understand the implementation science associated with a teledermatology program, and it will be the first to study VA apps that are intended to interface directly with existing clinical care pathways. The research will have strategic importance for VA and OCC as additional mobile apps serving other clinical needs, particularly those that directly interact with clinical care of patients, are rolled out in the future. Additionally, we believe that studying the process within the paradigm of OTIE and the REP framework will allow the findings to be broadly applicable to other healthcare organizations.

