Data analysis. Primary data will be collected and analyzed by CAPER and shared in aggregate with the PIs and other investigators. Stepped wedge - cluster randomized trials (SW-CRTs) need to employ data analysis strategies that account for the causal structure implied by this design and mitigate its potential shortcomings. Two related issues which may confound the treatment effect are the within-cluster correlation and potentially significant secular trends in the outcomes of interest given the long duration of the trials (2.5 years). In fact, the exposure of each cluster to both the control and intervention allows the researcher to partially exploit the within cluster variance towards estimation, which renders this type of trial less sensitive to the intra-cluster correlation coefficient. To further ensure that these confounding factors are properly handled, we will analyze the data using mixed models that allow for time fixed effects and cluster random effects.

Second, we are interested in the average effect of the treatment among compliers (patients who only receive the treatment as a direct result of their exposure to the intervention), referred to as the Local Average Treatment Effect (LATE). This effect better reflects the efficacy of teledermatology compared to regular practice. In order to estimate LATE, we will follow an instrumental variable (IV)-based two-stage residual inclusion (2SRI) procedure.

Finally, we will also conduct an intent-to-treat analysis, yielding an estimate of the average effect of being randomized to receive one of the telederm apps (average treatment effect). From a policy perspective, this effect can be interpreted as the efficacy of deploying an app in real-world outpatient clinics, where overall uptake to clinical practice is likely less than 100%.

Aim 2

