10.0 Sample Size and Eligibility Criteria

10.1 ENROLLMENT TARGET: How many people will you enroll:

50

If there are multiple participant groups, indicate how many people will be in each group:

Aim 1 will collect aggregate data relating to access exclusively by Veteran patients to VHA dermatology. While some characteristics such as Veteran patient rurality and location will be monitored for individual encounters, the research has no direct or indirect patient contact or involvement. Our randomized study of a total of 60 nationally distributed VA facilities will include encounter data from Veteran patients who are expected to generally reflect the diversity of VA's patient population with respect to age, gender, race and ethnicity. Children will be excluded since VHA does not serve pediatric populations and since children are not a target population for the apps.

Aim 2, as part of formative evaluation, will involve structured interviews and surveys of VHA staff at three early adopter sites, including VISN and facility organizational leadership (VISN Telehealth Leads, Dermatology Chiefs, Facility Telehealth Coordinators), support staff (Information Security Officers, Clinical Application Coordinators, Information Technology specialists), and clinical end-users (primary care providers, Telehealth Clinical Technicians, dermatologists) and clinical support staff (Medical Support Assistants). Thus we anticipate 16-17 subjects will participate at each site. Since there are 3 sites that will participate in the formative evaluation, we estimate that 50 subjects will participate via surveys and interviews overall. For the formative evaluation, some but not all subjects may be Veterans, and will

reflect the composition and diversity of VHA's workforce. For sub aim 2.2, 28 site leads will receive the bi-monthly report and 4 of these 28 sites will be asked to participate in a semi-structured interview. Two will have high usage of the app and two with low to no usage of the app.

10.2 TOTAL PARTICIPANTS: For multicenter studies, how many people will be enrolled in total:

50

10.3 SAMPLE SIZE JUSTIFICATION: Explain how and why the number of people was chosen. For multi-site studies, this is referring to the number that will be enrolled across all sites:

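### On its natural reading, the planned Aim 1 model gives too narrow a confidence interval for the average app effect if that effect differs between facilities, as the expected uneven adoption implies

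*Combined protocol and SAP*

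**What the plan says.** Section 8.13 (Statistical Methods, Aim 1) describes the model in one sentence: "we will analyze the data using mixed models that allow for time fixed effects and cluster random effects". The stated reasons are within-cluster correlation and secular trends over a trial of 2.5 years. The same section defines the intent-to-treat target as the average effect of being randomized to an app and expects that "overall uptake to clinical practice is likely less than 100" percent. It names no facility-by-app variance, robust variance or small-sample correction.

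Other sections expect facilities to differ:

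- Section 8.4, on past experience: "Implementation and adoption of telehealth, including teledermatology, in the VHA has proven to be a slow and heterogeneous effort", and "teledermatology has been actively adopted and thriving at some sites, while being neglected or failing at others".
- Section 8.3 says that an app's impact depends on implementation and adoption as well as on the app itself.
- Section 8.2 (Aim 2) plans to "stratify analyses of primary outcomes from Aim 1 based on degree of adoption". The Sub-Aim 2.2 text in sections 8.9 and 8.13 plans to examine whether the apps work better at sites that reach more milestones.
- Section 10.1, on the four randomized sites chosen for interview: "Two will have high usage of the app and two with low to no usage of the app".
- Section 8.2 (Aim 1) will also "determine whether a differential effect occurs for facilities with some pre-existing teledermatology relative to those that had none".

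Section 8.13 opens its Aim 1 text by saying that too few sites took part, partly because of the pandemic. The plan could not be followed, and a study of factors linked to consult completion took its place.

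**The concern.** If impact depends on adoption, and adoption runs from heavy use to none, the effect of being offered the app differs from facility to facility. The target is the average of those facility effects. Its uncertainty has two parts: noise in each facility's outcomes, and the spread of true effects over a limited number of facilities (36 for VA Telederm, 24 for My Telederm).

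The natural reading of the planned model is quarter effects, a random facility level and one app effect. That model carries only the first part. As consults per facility increase, its standard error keeps shrinking as though every facility responded alike, while the second part does not shrink at all. At stake is the stated precision of the Aim 1 average effect.

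**Working it through.** **The plan's own figure.** Section 10.3 says the trials are well powered in most scenarios for a 10% difference from baseline. It gives no alpha, power, SD, ICC, consult volume or effect variance, so the statement cannot be reproduced. What follows checks the mechanism only.

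**Inputs from the documents.** There are 36 and 24 facilities (8.2). Steps last three months (8.3) over a two-year rollout (8.2), so 24/3 = 8 steps. The trial lasts 2.5 years (8.13), so 30/3 = 10 quarters.

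**Assumptions.** Outcome SD 1; ICC 0.05, so between-facility variance τ² = 0.05 and within-facility variance σ² = 0.95; m consults per facility-quarter, from 50 to 600; SD of the app effect across facilities η = 0.05 or 0.10.

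**Formulas.** For facility i, let x_i be its 0/1 app indicator over the 10 quarters, X_i = [I, x_i], and V = τ²J + (σ²/m)I.

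- Model variance of the app effect: the last diagonal element of A⁻¹, where A = Σ X_i'V⁻¹X_i.
- True variance of the same estimate when effects vary: the last diagonal element of A⁻¹BA⁻¹, where B = Σ X_i'V⁻¹(V + η²x_i x_i')V⁻¹X_i.
- Coverage = P(|Z| < 1.96 × SE_model / SE_true).

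**Results, 24 facilities.**

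| Consults per facility-quarter | η | SE_true / SE_model | Coverage of nominal 95% interval |
|---|---|---|---|
| any | 0 | 1.00 | 95% |
| 50 | 0.05 | 1.05 | 94% |
| 100 | 0.05 | 1.11 | 92% |
| 100 | 0.10 | 1.37 | 85% |
| 300 | 0.05 | 1.29 | 87% |
| 300 | 0.10 | 1.91 | 69% |
| 600 | 0.05 | 1.53 | 80% |
| 600 | 0.10 | 2.51 | 56% |

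With 36 facilities the rounded coverage is the same in every row, because both variances fall in proportion to the number of facilities and their ratio barely moves.

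**Hand check (24 facilities, m = 300, η = 0.05).** SE_model = 0.0129 and SE_true = 0.0167, a ratio of 1.29. Then 1.96/1.29 = 1.52, and P(|Z| < 1.52) = 87%. A simple approximation agrees: √(0.0129² + 0.05²/24) = √(0.000166 + 0.000104) = 0.0164. The term η²/24 is the part that more consults cannot reduce.

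**Sensitivity to how the data are fitted.** The table describes a consult-level fit. If facility-quarter means are fitted, the residual absorbs some of the heterogeneity and the loss is smaller. With 36 facilities, 9 steps, 200 consults and η = 0.10, coverage is 83% for means against 75% at consult level.

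**Do the remedies work?**

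- Facility-clustered standard errors with a t reference on (facilities − 1) degrees of freedom gave simulated coverage of 94–95%.
- A random app effect, with 200 consults and 150 fits per setting, gave 94.7% (36 facilities) and 96.7% (24) at η = 0.10. The intercept-only model gave 81% and 85%. Simulation error here is about 2 to 4 points, and some fits gave boundary or convergence warnings.

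**The case against.** The strongest case on the other side has five parts.

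1. **The plan was set aside.** Section 8.13 says so, and nothing in the documents shows that this interval was or will be produced. This stands and limits the point to the written plan.

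2. **The common effect is read from silence.** The section is a brief summary, Aim 1 is analysed under another centre's IRB approval, and the phrase about cluster random effects could cover a random app effect. This also stands in part. A reader might infer that the plan fixes one effect for all facilities, but it does not say so. A random facility level is only the natural reading, given the purposes stated.

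3. **The size is assumed.** The documents give no effect variance, and section 8.4 describes past telehealth across the VHA, not app effects at the selected sites. An SD of 0.10 would be severe if the average effect were 0.10 SD: with non-negative effects symmetric about that mean, half the sites would have to be at zero and half at double. This stands. The premise does not rest on section 8.4 alone, however, because sections 8.2, 8.3 and 10.1 look ahead to uneven adoption in this rollout.

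4. **Heterogeneity is already addressed.** Stratified analyses and a complier-effect analysis are planned. They show that a uniform response is not taken for granted, but they do not widen the interval for the overall average.

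5. **No false claim of benefit is shown.** A reader might infer excess false positives. The documents do not support that: if the app does nothing anywhere, uneven uptake creates no variation in effect and no excess error from this source. Nor does an assumed average effect of 0.10 SD become doubtful at 300 consults and 24 facilities: 0.10/0.0167 = 6.0 at η = 0.05, and 0.10/0.0247 = 4.0 at η = 0.10.

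**Conclusion.** The point holds in conditional form. If app effects differ between facilities, as the protocol's expectation of uneven adoption implies, a model with quarter effects, a facility intercept and one app effect reports too narrow an interval for the average intent-to-treat effect. The loss ranges from negligible (about 94% coverage with 50 consults and η = 0.05) to large (56% with 600 and η = 0.10). It rests on the assumed SD, ICC, volume, effect variance and a consult-level fit, and it vanishes when effects do not vary.

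The harm is overstated precision. A reader might also infer that My Telederm is hit harder because it has fewer facilities, but coverage is the same for 24 and 36. Nor do the documents show that any reported interval is wrong.

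**What to change.** In section 8.13, for any stepped-wedge estimate of the app effect, specify one of the following:

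- facility-clustered standard errors with a small-sample correction, such as a t reference on (facilities − 1) degrees of freedom; or
- a facility-level random app effect, allowed to correlate with the facility intercept.

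In either case report the between-facility SD of the app effect, which also bears on Aim 2's question about adoption. In section 10.3, state whether the power claim allowed for this variation.

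The cost is a few sentences, at most one extra variance and its covariance, and a wider interval. With 24 facilities, 300 consults and η = 0.05 the standard error goes from 0.0129 to 0.0167. A random app effect may also be estimated at its boundary; if its variance is estimated as zero, the interval is essentially unchanged.

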VA Telederm is anticipated to be ready for national release in January 2017 and *My Telederm* in the spring of 2018, as part of VA’s Office of Connected Care operations. Beforehand, technical field testing will occur at San Francisco, Providence and Denver VHA facilities. For national rollout, each app will be targeted to sites that are clinically appropriate and best positioned to benefit from the app. Within these sites, the apps will be released in three month intervals according to allow a cross-sectional stepped-wedge cluster randomized trial for each app. We anticipate the affected population will represent VA’s as a whole.

The impact of teledermatology apps depends not only on their intrinsic effectiveness, but also on successful implementation and adoption by as many target sites and end-users as possible who then maintain the practice. Outcomes may be organized within the RE-AIM Framework, which encompasses multiple domains necessary for translating innovation into real-world practice. The Reach and Effectiveness domains are addressed in Aim 1; The Adoption, Implementation and Maintenance domains are the focus of Aim 2.

Aim 1 will assess each app’s effect on Veterans’ access to dermatology in a stepped-wedge cluster randomized trial. Corporate Data Warehouse (CDW) data pertaining to access will be collected remotely by the Center for Access Policy, Evaluation and REsearch (CAPER) under its own IRB approval. Multiple measures reflecting different aspects of access will be evaluated to achieve a comprehensive and accurate evaluation of each app’s impact. Aim 2 will focus on measuring the degree to which each app was implemented. Using semi-quantitative interviews and surveys of key VA staff members at the three early adopter sites (San Francisco, Denver and Providence VA Medical Centers) involved in technical testing as well as data in CDW and OCC databases, we will monitor implementation and identify organizational, individual, and app-specific factors that affect each app’s overall impact.

8.4 BACKGROUND AND SIGNIFICANCE: Briefly provide the background and significance of this study (e.g. why is this study needed) (space limit: one half page):

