8.5 PRELIMINARY STUDIES: Briefly summarize any preliminary studies relevant to your proposed research (space limit: one half page):

The proposed research is to assess the implementation and impact of mobile apps that are in the final stages of development, validation and checks for compliance with VA's privacy and safety requirements. In anticipation of the stepped-wedge cluster randomized trial, all VA facilities were examined for teledermatology activity relative to total dermatology activity.

The inclusion criterion for the first trial (*VA Telederm*) was that a site had a minimum of 0.1% and < 8.8% of its total FY2016 dermatology encounters under secondary stop codes 695/696 (teledermatology readings). VA

medical centers with no 695/696 activity in FY2016 or with zero full-time equivalent dermatologists were excluded since these sites likely lack the expertise, support and infrastructure to feasibly adopt teledermatology during the study period. In total, we identified 36 sites eligible for *VA Telederm*, teledermatology constituting between 0.1% and 8.8% of all dermatology encounters.

Conversely, the inclusion criterion for the second trial with *My Telederm* was that a site had $\geq 8.8\%$ of all FY2016 dermatology encounters under secondary stop codes 695/696. This indicated considerable pre-existing experience with consultative teledermatology and the likely presence of dermatology reader and support personnel needed to implement *My Telederm*. We identified 24 sites where teledermatology constituted 8.8% to 100% of total encounters.

In Aim 1, apps will be disseminated according to the stepped-wedge cluster randomization scheme determined by this research project, but otherwise is under the control of VA's Office of Connected Care as part of its operational plan to disseminate the apps to the clinical field. The main outcomes are measures that serve as proxies for access to dermatology services, and these are stored in VA's Corporate Data Warehouse (CDW) which is remotely accessible.

8.6 * TREATMENT PROTOCOL: Is this a treatment study, i.e. does this study intend to provide treatment to individuals with a medical or psychological condition: (REQUIRED)

Yes No

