If the instruments are not complete or not available because they will be developed as part of this study, describe the basic content or include an outline and submit the final versions to the IRB with a modification for approval prior to use.

- 1) Site Information Report (revision attached)
- 2) Site Process Guide (attached)
- 3) Organizational Readiness for Change (ORC) Survey (revision attached)
- 4) Initial Interview Guide (attached)
- 5) Bi-Monthly Site Report (survey revision attached)
- 6) Follow-up Interview Guide (Allows participants to expand on the same areas covered by the bi-monthly site report)
- 7) Program Sustainability Index (survey revisions attached) Now VA T Program Sustainability index (attached) and My T Program Sustainability index (attached)
- 8) Sustainability Interview Guide (attached-Allows participants to expand on the same areas covered by the PSI survey)
- 9) Bi-Monthly Site Report for National Sites (attached)

Telephone/Email Consent Scripts for Contacting Subjects:

- 1) Email consent script (introduction and consent to ORC, both Bi-monthly reports, and Program Sustainability Index surveys)
- 2) Telephone consent script (introduction and consent to Site Process Guide, Initial Guide, Follow-up Guide, and Sustainability Guide)

Attach any unpublished instruments in the 'Other Study Documents' section of the Initial Review Submission Packet form after completing the study application. Published instruments should NOT be attached.

8.12 * BIOSPECIMEN COLLECTION: Are you drawing any blood or collecting other biosamples (e.g. tissue, buccal swabs, urine, saliva, hair, etc.) for analysis under this protocol and/or storage for future research: (REQUIRED)

Yes No

8.13 STATISTICAL METHODS: Briefly summarize the methods and types of analyses that will be performed:

Aim 1-Due to a lack of participation by sites during the study which was in part conducted during the novel coronavirus (COVID-19) pandemic, we were not able to follow the analysis plan for Aim 1 described below. Instead we focused on understanding factors associated with successful completion of consults with the mobile apps, examining differences between rural and urban Veteran users.

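### Low site participation does not by itself rule out the planned intention-to-treat analysis that section 8.13 drops, and the app-user analysis that replaces it cannot test the access hypothesis

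*Combined protocol and SAP*

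**What the plan says.** Section 8.13 opens its Aim 1 text with a deviation. Because of a "lack of participation by sites during the study which was in part conducted during the novel coronavirus (COVID-19) pandemic", the Aim 1 analysis plan was not followed, and no part of it is excepted. The replacement is given in one sentence: "Instead we focused on understanding factors associated with successful completion of consults with the mobile apps, examining differences between rural and urban Veteran users."

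The plan that was set aside follows directly. It has mixed models with time fixed effects and cluster random effects, an instrumental-variable estimate of the effect among compliers, and an ITT analysis "yielding an estimate of the average effect of being randomized to receive one of the telederm apps (average treatment effect". The ITT is justified as describing real-world clinics "where overall uptake to clinical practice is likely less than 100" per cent.

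Other sections bear on whether that ITT depends on site participation:

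- Section 8.2 defines the primary outcome as "Consult and appointment completion times for both teledermatology and in-person consults", split by new and established patients.
- Section 8.3 says Corporate Data Warehouse (CDW) "data pertaining to access will be collected remotely by the Center for Access Policy", Evaluation and Research (CAPER).
- Section 8.5 says the "apps will be disseminated according to the stepped-wedge cluster randomization scheme determined by this research project", "but otherwise is under the control of" the Office of Connected Care.

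Section 8.2 plans 36 facilities for VA Telederm and 24 for My Telederm. Section 10.1 gives the total as 60 and separately sends a bi-monthly report to 28 site leads. Section 8.9 (Sub-Aim 2.2) says that report is asked of randomised sites.

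**The concern.** The stated reason does not cover everything that was dropped. Low participation weakens the complier analysis, because assignment then changes the care of few patients, and it costs power throughout. It does not remove an ITT, whose groups are fixed by assignment and whose outcomes arise in routine care whether or not a site opens the app.

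The replacement answers a different question. It describes which app consults were completed and how rural and urban users differ. The section 8.1 hypothesis concerns access at implementing sites relative to control sites.

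At stake is the randomised evidence on both apps. As the text stands, a reader cannot tell whether the ITT was impossible or was possible and not done. The summary in section 4 still says the study will have documented effectiveness. Section 8.2 (Aim 2) and section 8.13 (Sub-Aim 2.2) still stratify Aim 1 or main results by adoption or milestones to judge whether the apps work better where implementation went further.

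**Working it through.** **Site counts.** Inputs: 36 and 24 (section 8.2), 60 and 28 (section 10.1). 36 + 24 = 60, so the planned total reproduces. 28/60 = 47%. The 28 is the number of site leads sent a report, not a count of sites randomised, and it is not split by app. No section gives the number of sites randomised, released or participating for either app.

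**What the ITT needs, against what low participation removes.**

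- *An assigned release date for each site.* Participation does not create or remove this. Section 8.5 says the project sets the scheme, but it is prospective and leaves other control of dissemination to the Office of Connected Care. Whether dates were assigned and followed is not stated.
- *Outcomes in every site and period, before and after the assigned date.* These come from the CDW, are collected remotely, and cover in-person consults. A site that never used the app still contributes.
- *Full uptake.* Not needed. Section 8.13 expects less.

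Only the first requirement could defeat the ITT, and section 8.13 does not say that it failed.

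**What the replacement can estimate.** App users exist only where and when an app is in use, so every observation is exposed. There are no control sites or control periods, and inclusion depends on use, which follows release. Rural and urban users are not randomised groups. The analysis therefore yields associations among users and no effect of either app on access.

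**What low participation does cost.** Suppose a share p of assigned sites uses the app and there is no effect elsewhere. Then the ITT effect is p × full effect. With the 10% difference from section 10.3 and assumed values of p:

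- p = 0.75: 0.75 × 10% = 7.5%
- p = 0.50: 0.50 × 10% = 5.0%
- p = 0.25: 0.25 × 10% = 2.5%

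The effect is diluted but can still be estimated. The precision of the ITT cannot be derived: section 10.3 claims adequate power for 10% without giving alpha, power, variance, intracluster correlation or cluster size.

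**Tally.** Randomised app trials planned: 2. Randomised effect estimates in the revised section 8.13: 0.

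**The case against.** The strongest reply is that the deviation is disclosed and that Aim 1 is planned elsewhere. Section 8.13 says what was not done, why, and what replaced it. Section 4 says Aim 1 is not the focus of this application. Sections 8.2, 8.9 and 13.0 place its data and monitoring with CAPER under separate approval, and the section 8.13 field asks only for a brief summary. The counts and the full reason may be in CAPER's record. If lack of participation means that the stepped rollout never took place, the statement that the plan could not be followed is simply correct.

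Much of this stands. It limits the point to what this document supports, and a cross-reference to CAPER's record would be an adequate answer. It does not remove the point. The change is stated here without a reason that reaches the ITT, and other parts of this document still depend on the dropped result.

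Three stronger readings are tempting and not supported:

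- *That a feasible ITT was left out.* References in section 8.9 to randomised sites, and in section 10.3 to heavy and light app use over the last year, suggest that assignment and release occurred. They do not show that releases followed assigned dates.
- *That 28 sites were randomised and the rest of the 60 were lost.* The 28 belongs to a reporting activity. Subtracting it from 60 does not give a trial-flow figure.
- *That no randomised result exists anywhere.* The absence is established for this document only.

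**Conclusion.** The point holds and should be fixed. Low site participation, as stated, is not sufficient reason to drop the ITT, and the app-user analysis cannot replace it as a test of access relative to control sites. The size is structural: two planned randomised comparisons become none in the revised text, while the section 4 effectiveness statement and the stratified analyses in sections 8.2 and 8.13 remain. No numerical loss can be computed from the documents.

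Confidence is moderate. Feasibility rests on two facts the documents do not give: whether release dates were assigned, and whether the rollout followed them. The dilution figures are illustrative and assume no effect at sites that do not use the app.

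**What to change.** 1. For each app, report the planned stepped-wedge ITT estimate with its confidence interval on the primary CDW access outcome. Include every site assigned a release date, analysed by that date. If no dates were assigned, or the schedule was not carried out, state that as the reason; a cross-reference to CAPER's record is enough. Either way, give the numbers randomised, released and participating per app, and say how the 28 report sites relate to the planned 60.
2. Label the rural-urban analysis of app users post hoc and non-randomised.
3. Make the section 4 effectiveness statement and the stratified effectiveness analyses in section 8.2 (Aim 2) and section 8.13 (Sub-Aim 2.2) conditional on item 1, or withdraw them.

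A sensitivity analysis truncated at the start of the pandemic is optional.

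Cost: text changes in sections 4, 8.2, 8.13 and 10.1. If the ITT can be run, add at least one primary-outcome model per app, or 2 apps × 2 patient groups = 4 when new and established patients are modelled separately, before any rurality strata. The documents do not say whether CAPER has already extracted the data. The ITT may be imprecise and diluted, and common time effects may not absorb pandemic shocks that differ by site. It should be read from its confidence interval and not as evidence of no effect. If no dates were assigned, the cost is text only.
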